8.2 Data Safety Monitoring Plan

There are no primary or secondary endpoints. Patients undergoing vascular surgery as part of their routine clinical care will have a blood collection before and after surgery to help identify future markers in their blood related to clotting and bleeding episodes. The proposal is deemed to be low risk for subjects. Safety information will be collected via telephone at 30 days after the surgery, case report form, and/or scheduled follow-up visits as part of standard of care.

PI will conduct interim monitoring of accumulated data from research activities to assure the continuing safety of participants, relevance of the study question, appropriateness of the study, protocol compliance and integrity of the accumulating data. The PI in conjunction with NYU IRB will be responsible for monitoring the data and conducting safety reviews at a minimum of every 12 months when annual re-approval is sought. Any unanticipated serious adverse event will be reported to IRB within 72 hours. During the review process, the PI and NYU IRB will evaluate whether the study should continue unchanged, require modification/amendment, or close to enrollment.

9. Confidentiality:

Study is for research purposes only. Individual result will not be given back to study participant. This will include information from final results of the study, interim results of the study and incidental findings. Research result will never occur in medical records. Confidentiality will be preserved to the fullest extent by the research team. All data will be stored with a unique code that does not identify the subject. Furthermore, data will be saved using a double electronic lock. All physical data will also be kept under double physical lock. Access to the data will be given to the study personnel only.

10. Appendix A: Schedule of study related procedure

	Pre-op Period	POD 2 (+/- 1 day)	Discharge	Post-op Appointment follow-up	Long-term follow-up
Eligibility	X				
Informed consent	X				
Demographics	X				
Medical history/status	X	X	X	X	X
Medication use	X	X	X	X	X
Vital signs	X	X	X		
Standard lab results	X	X	X	X	X
Troponin	X	X			

ECG	X	X			
Blood draw	X	X		X	
Urine sample	X			X	
Endothelial dysfunction assessment	X	X		X	
QOL assessment	X			X	X
Diet questionnaire	X				
Lifestyle assessment	X			X	X
Medication adherence	X			X	X
Hospitalization assessment			X	X	X
Endpoint assessment		X	X	X	X
Cognitive Function Test					X

1. Pre-operative period
 - 1.1. Determine eligibility
 - 1.2. Obtain informed consent
 - 1.3. baseline interview with the subject and review the clinical history, demographic information, lifestyle assessment, QOL assessment, medication use and adherence
 - 1.4. Vital signs
 - 1.5. Obtain ECG
 - 1.6. Measure troponin
 - 1.7. Urine sample
 - 1.8. Blood sample
 - 1.9. Endothelial function assessment

2. Post-operative day # 2 (+/- 1 day):
 - 2.1. review medical status
 - 2.2. Medication use
 - 2.3. Vital signs
 - 2.4. Review standard lab tests
 - 2.5. Obtain ECG
 - 2.6. Measure troponin
 - 2.7. Blood sample
 - 2.8. Endothelial function assessment
 - 2.9. Endpoint assessment

3. Day of discharge
 - 3.1. review medical status

- 3.2. Medication use
- 3.3. Vital signs
- 3.4. Review standard lab tests
- 3.5. Hospitalization assessment
- 3.6. Endpoint assessment

4. Post-op Appointment follow-up):
 - 4.1. review medical status
 - 4.2. Medication use and adherence
 - 4.3. Review standard lab tests
 - 4.4. Blood sample
 - 4.5. Urine sample
 - 4.6. Endothelial function assessment
 - 4.7. Lifestyle and QOL assessment
 - 4.8. Hospitalization and assessment
 - 4.9. Endpoint assessment

5. Long term follow up (q 6months [+/- 2 months]):
 - 5.1. review medical status
 - 5.2. Medication use and adherence
 - 5.3. Review standard lab tests
 - 5.4. Lifestyle and QOL assessment
 - 5.5. Hospitalization and assessment
 - 5.6. Endpoint assessment
 - 5.7. Cognitive function test (will be assessed once)
 - 5.8. Question regarding history of dementia (will be assessed once)
 - 5.9. Vita status assessment

11. References:

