Blood samples will be assigned a unique code number and stored in the PI's lab without any identifying information other than a code number. The unique code number will not be based on any information that could be used to identify the subject (for example, social security number, initials, birth date, etc.). The master list linking names to code numbers will be kept in a locked file cabinet, separate from all research information placed under double lock and key at the PI's office at NYU Skirball 9th floor. All confidential data will be stored with a unique code as an identifier and will be protected by a double electronic lock. All physical data will be kept under double physical lock. Access to the data will be given to the study personnel only.

Samples will be stored for no more than 10 years following completions of the study. Samples will be used for testing other potential biomarkers in patient plasma and/or serum related to other endpoints not specified in the protocol (e.g. cancer, metabolic disease, etc.). Genetic testing will not be conducted on stored samples. Results of the future research will not be shared with the subjects or their study doctor, and will not become part of the medical records.

Subjects can request for withdrawal of samples at any time by contacting PI [name] in writing. His mailing address is [name]. Withdrawing

Authorization only affects uses and sharing of information after written request has been received, and subject may not withdraw his/her Authorization for uses or disclosures that have previously been made or must continue to complete analyses or report data from the research.

f. After Surgery and Follow Up

Starting on the day of surgery and continuing throughout hospitalization, a physician monitors the patient's course for clinically evident cardiovascular events (MI, stroke, TIA, major bleeding, kidney disease, or any surgical complication). Blood collections and/or ECG's that are performed as part of routine care and/or for study purposes will be recorded and may be used to help ascertain whether a cardiovascular and/or bleeding event has occurred. After hospital discharge, patients will be contacted by telephone (or during their routine clinical follow-up) at 30 days and every 6-month thereafter out to 5-years. At the patients' follow-ups they will be asked questions about their health, lifestyle, and medication use.

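### Section 9 bars return and charting of results with no exception; this contradicts the cognitive-result disclosure in section 4.f and, read literally, covers any ECG or troponin done only for the study

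*Combined protocol and SAP*

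**What the plan says.** Section 9 sets three rules on results. On return to the participant: "Individual result will not be given back to study participant". On the scope of that rule: "This will include information from final results of the study, interim results of the study and incidental findings". On the chart: "Research result will never occur in medical records". It then limits data access to study personnel. It states no exception.

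Section 4.f (After Surgery and Follow Up) says that a physician follows the patient in hospital, monitoring the "course for clinically evident cardiovascular events (MI, stroke, TIA, major bleeding, kidney disease, or any surgical complication". It adds that blood collections and ECGs "performed as part of routine care and/or for study purposes will be recorded and may be used to help ascertain" whether an event has occurred. Later in the same section, participants whose remote testing shows signs of cognitive impairment are to be told and offered a letter to their primary care provider.

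Appendix A, the schedule of study procedures, lists an ECG and a troponin before surgery (items 1.5 and 1.6) and again on POD 2 (items 2.5 and 2.6). On POD 2 these are separate from the review of standard laboratory tests (item 2.4).

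Section 8.2 says: "PI will conduct interim monitoring of accumulated data from research activities to assure the continuing safety of participants". It provides for "conducting safety reviews at a minimum of every 12 months when annual re-approval is sought", and states: "Any unanticipated serious adverse event will be reported to IRB within 72 hours".

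**The concern.** Most measures in this study (platelet function, coagulation, inflammation, RNA and DNA profiling) are exploratory and have no established clinical use, so a no-return rule suits them. Section 9, however, is worded for results in general, and two other kinds of result are generated under the same protocol.

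The first is the cognitive test result. The plan promises to return it in one section and forbids return in another, so staff cannot comply with both.

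The second is an ECG or troponin done around surgery because the schedule calls for it. If routine care would not have included that test, its result exists only as study data. Should it suggest an infarction without symptoms, staff who follow section 9 to the letter would not tell the patient and, on one reading, would not chart it. Staff who did either would depart from the protocol. That choice should be settled in advance rather than on the ward.

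**Working it through.** No calculation settles this point, so the relevant provisions are compared.

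**1. Is there a conflict within the text?** Yes, for cognitive results. Section 9 says individual results do not go back to the participant. Section 4.f says the participant will be informed of signs of impairment. The offered letter also sits awkwardly with the chart rule, since a letter to a provider would ordinarily be filed in that provider's records. Section 9 does not refer to section 4.f, and section 4.f does not say that it overrides section 9.

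**2. Could an ECG or troponin be study-only?** The text allows for it without establishing it. Section 4.f speaks of tests done for routine care, for the study, or both. Appendix A tells staff to obtain the two tests and lists them apart from standard laboratory review on POD 2. A participant whose routine care omits one of them would therefore have it done for the study alone. The share is not stated for either time point.

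**3. Does another provision give such a result a route to someone who can act on it?**

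| Provision | What it covers | Route for a single study-only result? |
|---|---|---|
| 4.f, physician monitoring | Events that show themselves clinically | Not stated; a silent infarction does not show itself |
| 4.f, use of ECGs and blood tests | Recording and ascertaining events | No instruction to report to the treating team |
| 8.2, PI monitoring | Accumulated data, with a stated minimum of one review every 12 months | No; not a per-result rule |
| 8.2, 72-hour report | Unanticipated serious adverse events, to the IRB | No; different trigger and recipient |
| 4.f, cognitive disclosure | Cognitive testing only | No |

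**4. Does section 9 forbid telling the treating team?** No. Sections 4.d (Genetic Profiling) and 4.e (Future Sample Storage) name the physician or study doctor when they bar disclosure, and section 9 does not. The treating team is therefore not excluded by name. What is missing is a direction to tell them.

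**5. Can the number of affected results be given?** No. Multiplying the 350 planned participants by the scheduled tests would count tests, most or all of which may be routine care and already in the chart. Re-enrolment after more than 90 days, allowed under the inclusion criteria, means that even such a product might not be a ceiling. The documents give no basis for the share that is study-only or the share that would be actionable.

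**The case against.** The strongest reply is that the ECG and troponin part rests on a premise the documents never confirm. If every scheduled test is also routine care, section 9 withholds nothing. That stands, and it is why this part is conditional.

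A second reply concerns wording. Research result is not defined and may mean only the exploratory assays. The mention of incidental findings belongs to the rule on return to participants, not to the separate sentence about the chart, so it does little to extend the chart ban to an ordinary ECG or troponin. This also stands. The bar on telling the participant is clear on its face, while the bar on charting is arguable.

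Third, section 4.f lets study ECGs and blood tests help ascertain events, and Appendix A places an endpoint assessment at the same POD 2 contact (item 2.9). This puts the results close to in-hospital monitoring, and a treating team told of an abnormality could order and chart its own test. This reduces the practical risk but is not an instruction to pass the result on.

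Fourth, the consent pages and case report form are not available here and may deal with return of results. Also, the background section describes the platelet phenotypes as already measured, so much of the cohort may be past the perioperative stage. The current text still provides for recruitment and re-enrolment.

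A reader might infer from section 9 that actionable perioperative results will be hidden from treating physicians and that patients will go untreated. The documents do not support that. Routine tests are already in the chart, section 9 does not exclude the treating team, and nothing prevents that team from repeating a test.

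None of these replies resolves the cognitive-result conflict. One might say that the specific promise in section 4.f overrides the general rule in section 9, but the plan does not say so.

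**Conclusion.** The point holds in a limited form. One part is definite: sections 9 and 4.f contradict each other on whether participants learn their cognitive results. The other part is conditional: if any pre-operative or POD 2 ECG or troponin is done only for the study, section 9 read literally keeps the result from the participant, arguably keeps it out of the chart, and leaves staff with no direction to tell the treating team.

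The conditional part assumes that at least one such test is study-only, that individual result includes an ECG or troponin, and that the material not available here does not already provide a route. The number of affected results may be small or zero and should not be quoted. This is a minor participant-safety point. It has no effect on the aims, endpoints or analysis, and it makes no claim that any patient would be harmed.

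**What to change.** Keep the section 9 ban as the default for the exploratory measures: platelet, coagulation, inflammation, RNA and DNA, endothelial function and tissue. Add to section 9, with a cross-reference in section 4.f:

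> Exceptions: cognitive test results as described in section 4.f; and clinically actionable ECG or troponin results obtained for the study (pre-op or POD 2), by the hospital's own critical-result criteria, which are reported to the treating team when available and may be entered in the chart.

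Section 4.f should also say which ECGs and troponins, if any, are done only for the study, and whether a study troponin is assayed at once or in batches. If it is batched, the second exception matters in practice mainly for the ECG. If no test is study-only, a sentence saying so makes the second exception unnecessary. The first is needed either way.

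The cost is an IRB amendment and a small task for existing staff, who would compare study ECG and troponin results with the hospital's criteria as they become available. It needs no added sample, assay or participant, and the analysis is unchanged.
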